***Methemoglobin to be collected at 6 hours only**

DAY 1-3 (0-72 h post-ROSC) DATA

During post-ROSC days 1-3, the following data elements will be collected by a physician coinvestigator/research assistant prospectively or by a research assistant retrospectively. Refer to chart for visual of when labs will be drawn.

- Plasma labs measured variably between 24 and 72 h (troponin, arterial blood gas, lactate, plasma nitrite level, neuron specific enolase, ascorbate, cardiolipin, plasma banking)
- Urine labs measured variably between 24 and 72 h (renal failure and nitrated fatty acid measurements)
- *Full Outline of UnResponsiveness (FOUR) Score (components below)
- Eyes
- Motor
- Brainstem
- Reflex
- *Glasgow Coma Score (GCS)
- Eyes
- Verbal
- Motor
- EEG interpretation
- Dominant background present
- Reactivity present
- Seizures present
- Seizure type
- Burst-suppression ratio
- Estimate of survival to hospital DC
- Median nerve SSEP
- Witnessed aspiration
- New suspected infection last 24h
- Infection type
- Sputum color
- Vent mode
- Set Vt
- Set PC
- PEEP
- FiO2 (Use % oxygen)
- Peak Pressure
- Plateau Pressure
- CXR last 24h read may be pneumonia
- Positive airway culture last 24h

- Vital Signs (VS) (highest and lowest for each)
- Time to follow commands (assigned once)
- SOFA (worst in prior 24h period; some components may be missing)
- Respiratory (when no PaO₂ is available for PaO₂:FiO₂ ratio, use SpO₂:FiO₂ ratio)
- Nervous (based on GCS below)
- Cardiovascular
- Liver
- Coagulation
- Renal
- Interventions
- Coronary angiography
- PCI
- ECMO
- CPR
- CABG
- Mechanical ventilation hours
- NIPPV hours
- 24h FiO₂ AUC
- Tracheostomy
- Medications (dichotomous for use not dose)
- Alteplase
- Anti-epileptic
- Midazolam infusion
- Intermittent Benzodiazapine
- Propofol infusion
- Intermittent Propofol
- Opiate infusion
- Intermittent opiate
- Neuromuscular blockade infusion
- Intermittent neuromuscular blockade
- Neurostimulants
- *Vasopressors
- *Inotropes
- Ketamine
- Steroids (hydrocortisone/methylprednisolone)
- Cumulative vasopressor index (CVI; worst in prior 24h period)
- *BUN (highest value in prior 24 h)
- *Creatinine (highest value in prior 24 h)
- Hb
- WBC
- platelets
- PT
- INR
- PTT
- Bilirubin
- AST

- ALT
- BNP
- SvO2 (%)
- venous PaO2
- venous PaCO2

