Research labs will be obtained by a study coordinator within 30 minutes of the assigned draw time. Labs will be run either within the UPMC Clinical Labs or the research labs of Drs. [name] or [name] as specified. We will also be collecting a small blood sample for an ancillary biomarker study for those subjects wishing to participate.

The final data to be collected will be the 90 d or discharge outcomes (whichever is later). Information that cannot be obtained by record review will be obtained either in person, or via a phone call by a member of the study team.

TABLE 1

Vital signs	Time from study drug start (hours)							
	0	3	6	9	12	24	48	72
Temperature	X	X	X	X	X	X	X	X
Heart Rate	X	X	X	X	X	X	X	X
Systolic Blood Pressure	X	X	X	X	X	X	X	X
Diastolic Blood Pressure	X	X	X	X	X	X	X	X
Mean Arterial Pressure	X	X	X	X	X	X	X	X
Arterial SBP	X	X	X	X	X	X	X	X
Arterial DBP	X	X	X	X	X	X	X	X
Arterial MAP	X	X	X	X	X	X	X	X
Pulmonary artery systolic pressure	X	X	X	X	X	X	X	X
Pulmonary artery diastolic pressure	X	X	X	X	X	X	X	X
Pulmonary artery mean pressure	X	X	X	X	X	X	X	X
Central venous pressure	X	X	X	X	X	X	X	X
Cardiac output	X	X	X	X	X	X	X	X
Vasopressors	X	X	X	X	X	X	X	X
Inotropes	X	X	X	X	X	X	X	X
Sedation	X	X	X	X	X	X	X	X
Neuromuscular blockade	X	X	X	X	X	X	X	X
Time from study drug start (hours)								
Labs (highlight represents UPMC Labs)	0	3	6	9	12	24	48	72
Troponin	X		X		X			
Arterial blood gas (ABG)	X		X		X			
Lactate	X		X		X			
Methemoglobin			X					
Neuron specific enolase (NSE)	X					X		
Plasma NO metabolites	X	X	X	X	X	X	X	X
Platelet mitochondria	X				X			
Ascorbate	X	X			X	X		
Cardiolipin	X	X			X	X		
Inflammation (integrin $\alpha 9\beta 1$ and CD11b)	X					X	X	X
Banked plasma	X	X	X	X	X	X	X	X
DNA for pharmacogenomics	X							
Whole blood pellet	X	X	X	X	X	X	X	X
Urine for renal failure markers and NO ₂ -cLA	X				X	X		
*DNA will be collected with the first scheduled blood draw after obtaining informed consent								

Outcomes

The following will be recorded at DC (+/- 3 days), and for follow up at day 30 (+/- 3 days) and day 90 (+/- 3 days) after OHCA:

*Survival

Cause of death

date/time of death

*CPC
*mRS
CPC-E
Barthel ADL
*NYHA Class
*Location of residence

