2.3.3. Dose Selection

A number of studies have reviewed the safety of iNO in adults primarily in the setting of acute respiratory distress syndrome (ARDS). A recent meta-analysis found improved oxygenation but also greater acute kidney injury (AKI) resulting from iNO use.²⁵ When this was examined by dose, AKI only resulted in those patients receiving higher cumulative doses of iNO (≥ 40 ppm for ≥ 48 h).²⁶ Our study will limit iNO to 20 ppm for 12h hence AKI is not expected though we will track BUN and creatinine on all subjects. A separate meta-analysis examining effects of iNO in

acute hypoxic respiratory failure in adults and children found no associated adverse events.²⁷ A study of iNO used in transport identified no adverse events associated with the drug.²⁸ Although iNO significantly increases methemoglobin (metHb) levels, the increase (0.3%) is clinically insignificant and not associated with toxicity²⁹ which is uncommon until levels of 20-30% (we will consider > 10% a significant and unexpected adverse event). The best predictor of significant metHb >4% (as < 0-3% is considered within normal range) is cumulative iNO dose of >2000 ppm * h.³⁰ In our study subjects will receive only 250 ppm * h. We will monitor methemoglobin as part of our study at 6h. Although iNO lowers pulmonary blood pressure it has not been linked to reduction in systemic arterial blood pressure. We will monitor blood pressure effects closely in our study given the inherent instability of cardiac arrest subjects.

Effects of iNO after cardiac arrest has been studied in 4 preclinical animal studies.⁸⁻¹¹ These published studies demonstrated benefit using iNO 40 ppm started within 2h of ROSC which is additive to therapeutic hypothermia⁸ as well as neuroprotection without temperature control.⁹ These animal models include mouse and pig models of asystole and ventricular fibrillation (VF). In addition iNO has been shown to protect in animal models of focal heart¹²⁻¹⁵ and brain¹⁶⁻¹⁹ injury. This is important since most of the mortality and morbidity after OHCA results from heart and brain injury.²⁰

Animal models of asphyxia²¹ and other focal brain ischemia reperfusion models demonstrate NO deficiency early in reperfusion lasting at least 6h and benefits from iNO.^{16,19}

Information from prior clinical trials of iNO are available by cross reference in the Mallinckrodt NDA 20-845 (letter authorizing cross reference is included with application).

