2.3.9 Rescue Medications

Hemodynamics will be stabilized using standard inotropic and vasopressor agents as needed in the ICU. There is no specific reversal agent for iNO. Methemoglobinemia can be reversed with treatment using methylene blue.

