2.4 STUDY ENDPOINTS

Primary

Composite of in-hospital death, unfavorable discharge location, NYHA class III/IV heart failure at the time of discharge*

*In the setting of pre-existing heart failure or prior residence in an unfavorable location there must be at least a 1 class decrement (eg NYHA III -> IV)

Secondary

Functional

- Survival to hospital discharge, 30 and 90 days after initial OHCA
- Favorable cerebral performance category (CPC) defined as 1 or 2 at discharge, 30 and 90 days after initial OHCA
- Favorable modified Rankin score (mRS) defined as 0-3 at discharge, 30 and 90 days after initial OHCA
- Favorable discharge destination or location of residence (30 and 90 days after OHCA) defined as home or acute inpatient rehabilitation
- CPC-E at hospital discharge, 30 and 90 days after initial OHCA
- Barthel Index of Independence in Activities of Daily Living (ADL) at discharge, 30 and 90 days after OHCA

Neurologic

- Estimated likelihood of good neurologic outcome (0-100%) assessed by an experienced (>3y) member of the PCAS team blinded to treatment assignment on day 3-5 post-ROSC.
- Development of malignant EEG during hospitalization

- Time (in hours) to awakening from ROSC; defined as following commands (all values > 96h assigned 100)
- FOUR Motor + Brainstem scores on days 1-3 (requires 30 min off sedation; exclude endpoint if not medically permitted to pause sedation or paralysis)
- Presence or absence of upper and lower extremity somatosensory evoked potential N20 on comatose patients obtained any time after post-arrest day 1.
- Absolute value 24h after ROSC and change in value (24h vs 0h) of neuron specific enolase (NSE)
- EEG burst suppression ratio and change in suppression ratio
- EEG presence of dominant continuous background and reactivity to photic or tactile stimulation.

Cardiovascular

- Heart rate and mean arterial pressure (preferably off the arterial line) at 0-12 (hourly), 24h of study drug
- Persistent need for vasopressors in the first 24h after ROSC; defined as any use of norepinephrine, epinephrine, phenylephrine, dopamine or vasopressin for ≥ 3 h after study drug is initiated
- Persistent need of inotropes in the first 24h after ROSC; defined as any use of epinephrine, dobutamine, milrinone or isoproterenol for ≥ 3 h after study drug is initiated.
- ECHO measures (absolute values at end of therapy (12h) and change in 12h vs 0h):
 - tricuspid valve regurgitant velocity (TRV)

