3.3 EXCLUSION CRITERIA

Exclusion criteria do not change any subgroups.

- Traumatic etiology of OHCA
- Prisoner
- Known pregnancy
 - o B-HCG screening is NOT REQUIRED for enrollment in women of appropriate age
- Hemodynamic instability defined as:
 - o > 1 recurrent arrest prior to enrollment
 - o Inability to maintain mean arterial blood pressure (MAP) > 65 using vasopressors and inotropes (ie actively up titrating medications or giving fluid bolus)
- Cerebral edema defined as:

- Head CT grey-white ratio < 1.2
 - Fixed and dilated pupils without another explanation
- Malignant EEG upon presentation (not required as screening) defined as:
 - Myoclonic status epilepticus
 - Non-convulsive status epilepticus
 - Generalized periodic epileptiform discharges
- ROSC >3h from time of ED arrival (Treatment allocation must be within 4h so anything that will prevent this is reason for exclusion)
- Alert and interactive patient with minimal evidence of neurologic injury
- Plan to extubate within 12 hours
- PCAS opinion that patient will die with >95% likelihood. This may be based on:
 - Multiple medical comorbidities
 - Late discovery of DNR or advanced directive
 - Terminal diagnosis (other than OHCA; may have caused OHCA)
 - Clinical judgement based on current exam and data
- Known intracranial hemorrhage or acute cerebral infarction; Head CT is NOT REQUIRED prior to enrollment
- Patient is known to be taking PDE5 inhibitors, sGC stimulator, or has a known diagnosis of Chronic thromboembolic pulmonary hypertension (CTEPH), pulmonary hypertension (PAH), or erectile dysfunction
- Known enrollment in another acute interventional trial

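### Measured MAP plus yes/no vasopressor and inotrope use can understate a pressure fall absorbed by a higher dose or a second vasopressor in subjects already on support

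*Combined protocol and SAP*

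**What the plan says.** Among the cardiovascular endpoints, section 2.4 lists "Heart rate and mean arterial pressure (preferably off the arterial line) at 0-12 (hourly), 24h of study drug" (the synopsis runs the hourly series to 13 h). Section 2.5.2 compares repeated measures by mixed models and names no pressor covariate and no baseline term.

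The companion endpoint is "Persistent need for vasopressors in the first 24h after ROSC; defined as any use of norepinephrine, epinephrine, phenylephrine, dopamine or vasopressin" for at least 3 h after study drug starts. Inotropes have a parallel endpoint, and epinephrine counts in both. Under 2.5.2 these dichotomous outcomes go to chi-squared tests.

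On treatment, section 2.3.9 says "Hemodynamics will be stabilized using standard inotropic and vasopressor agents as needed in the ICU". Section 3.3 excludes only subjects who cannot hold MAP above 65 without active up-titration or a fluid bolus, so a subject on a steady infusion is eligible.

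On data, the day 1-3 list in section 2.2 heads its drug block "Medications (dichotomous for use not dose", and that block includes vasopressors and inotropes. The same list has "Cumulative vasopressor index (CVI; worst in prior 24h period", and SOFA with a cardiovascular component. Neither CVI nor SOFA appears in the endpoint lists or in sections 2.5.1 to 2.5.5. Table 1 schedules vasopressors and inotropes at 0, 3, 6, 9, 12, 24, 48 and 72 h without saying whether dose is held.

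Section 2.3.3 states the intent: "We will monitor blood pressure effects closely in our study given the inherent instability of cardiac arrest subjects".

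**The concern.** MAP in this trial is a treated value. If study drug lowers pressure and the ICU team responds, part of the effect moves out of MAP and into support. The yes/no endpoints recover some of it: new starts, use prolonged past 3 h, and an added inotrope. They cannot recover a higher dose of an agent that is already running and would have continued, nor a second agent from the vasopressor list alone, such as vasopressin added to norepinephrine.

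At stake is the reading of the safety result. Similar MAP with similar yes/no use could be taken as no blood-pressure effect when dose had absorbed part of one.

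**Working it through.** The plan gives no MAP effect, SD, pressor dose or CVI effect, so there is no figure of its own to reproduce. What follows is an illustration.

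**Inputs from the documents.** 60 per arm (2.5.1); a 65 mm Hg floor (3.3, 6.4.5); two-sided 0.05 (2.5.2). Section 6.4.5 expects more than half of subjects to need over 50% FiO2 and/or vasopressors. It gives no figure for pressors alone, so shares from 35 to 80% are considered.

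**Assumed.** Unsupported MAP is normal with SD 12 and measurement noise SD 4. A pressor is given when unsupported MAP is below 65. Titration restores 100% or 80% of the deficit. The 0 h to on-drug correlation is 0.7. CVI rises one level per 6 mm Hg of deficit, capped at 4. 5% die on day 1 at random and are left out of the CVI test. MAP is tested on one on-drug mean, as a stand-in for the mixed model.

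**Step 1: how much of the fall MAP shows.** With full titration, measured MAP is max(U, 65), where U has mean m. Its mean excess over 65 is 12φ(d) + (m − 65)Φ(d), with d = (m − 65)/12. At a 50% share m = 65, so the excess is 12 × 0.399 = 4.79. After a 5 mm Hg fall it is 12 × 0.366 − 5 × 0.338 = 2.70. The visible difference is 4.79 − 2.70 = 2.09. The same formula gives 2.85, 1.39 and 0.74 at shares of 35, 65 and 80%. With 80% titration the difference is 0.8 × (full-titration value) + 0.2 × 5, that is 3.28, 2.67, 2.11 and 1.59 at 35, 50, 65 and 80%.

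**Step 2: power of the planned tests.** Untitrated, SD = √(144 + 16) = 12.65 and SE = 12.65 × √(2/60) = 2.31. Power is then Φ(5/2.31 − 1.96) = 58% for 5 mm Hg and 93% for 8. Simulated power at pressor shares of 50 / 65 / 80%:

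| Comparison | 5 mm Hg | 8 mm Hg |
|---|---|---|
| MAP, full titration | 33 / 23 / 13% | 63 / 43 / 19% |
| MAP, 80% titration | 44 / 37 / 32% | 80 / 72 / 62% |
| Yes/no vasopressor, as planned | 43 / 40 / 31% | 81 / 76 / 59% |
| Yes/no, adjusted for 0 h use | 52 / 48 / 37% | 90 / 83 / 68% |
| Day 1 worst CVI, adjusted for 0 h use | 46 / 43 / 34% | 89 / 85 / 74% |

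Adjusting MAP for 0 h MAP (5 mm Hg, full titration) gives 40 / 27 / 12%. Ranking day 1 deaths worst cuts CVI to 34 / 33 / 28% at 5 mm Hg.

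**Step 3: what CVI adds.** This is the chance that CVI is significant while MAP and yes/no are not. If only CVI is adjusted for 0 h, it is 13 / 15 / 18% at 5 mm Hg with full titration. With all three adjusted, over shares of 35 to 80%:

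| | Full titration | 80% titration |
|---|---|---|
| 5 mm Hg | about 4-13% | about 3-11% |
| 8 mm Hg | about 1-18% | about 1-8% |

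Under no effect it is about 3%. At a 35% share CVI adds essentially nothing.

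**Step 4: the gap in isolation.** Suppose the whole offset is one dose level in existing users. Yes/no then rejects at about 5%. Adjusted CVI has power of 50 / 61 / 70% if all users step up, 16 / 20 / 22% if half do, and 6 / 8 / 9% if a quarter do.

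**The case against.** The best defence is that measured MAP under usual care, read with support endpoints, is a legitimate choice. MAP of 65 or less for an hour despite fluids is a listed SAE tested under 2.5.4, so an uncorrected fall would be seen. A research assistant attends throughout dosing and the safety monitor reviews pressor need at least every 4 weeks. Sections 2.3.3 and 6.1.1 expect no systemic fall at this dose. The general rule in 2.5.2 for continuous data could be applied to CVI.

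Much of this stands. The oversight is real, but it is not a between-arm comparison. The general rule makes a CVI analysis possible but leaves open whether it is done and how pre-drug time and deaths are handled.

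A reader might go further in three ways that the documents do not support:

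- **That the plan is blind to hypotension.** It is not. MAP keeps reduced power, and new starts, prolonged use, added inotropes and uncorrected hypotension are all captured.
- **That comparing CVI closes the gap.** Its scoring is not given. If it is not graded by dose or number of agents it cannot help, and in the illustration it does not beat the 0 h-adjusted yes/no test at 5 mm Hg.
- **That the plan commits to treating similar MAP as proof of no effect.** No section says so. The risk lies in interpretation.

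**Conclusion.** The point holds as a limited one. A fall offset by more drug, or by a second vasopressor, in a subject already on support is understated in MAP and not seen by the yes/no vasopressor endpoint, and the collected measures that might show it have no named analysis. Every effect size above rests on assumed SDs, titration, correlation and a four-level dose scale.

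The more dependable gain is 0 h adjustment of the planned tests. It raises power in most scenarios, though not for MAP at an 80% share with full titration, and it does not make dose visible. CVI contributes materially only when pressor use is high or most existing users step up, and a null CVI result would not exclude an effect. The primary endpoint and sample size are untouched.

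**What to change.** In sections 2.5.2 and 2.5.4:

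1. Adjust the hourly MAP model for 0 h MAP, and the vasopressor and inotrope comparisons for use at 0 h. Both are already scheduled in Table 1.
2. State how CVI is scored. If it is graded by dose or number of agents, add one supportive rank-based comparison of day 1 worst CVI, adjusted for 0 h vasopressor and inotrope use. Report day 1 deaths separately by arm, with worst-rank scoring only as a sensitivity check. Give day 2-3 CVI descriptively, since dosing and wean end by about 4 + 12 + 1 = 17 h after ROSC.
3. State that MAP is read together with the support endpoints and CVI, and that similar MAP alone does not exclude a hypotensive effect. This sentence is worth having even if item 2 is dropped.

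The cost is SAP wording and one table, with no new data. The downsides are these: CVI is not marked essential and may be missing; its day 1 worst value can precede study drug by up to about 4 h; it does not capture fluids given to support pressure; and it is one more secondary test at unadjusted p<0.05, so it should be labelled supportive.

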2.5 STATISTICAL ANALYSIS

2.5.1 Sample Size Determination

Sample size calculations will be based on the primary composite endpoint and ascertained via a two sample test of proportions. The control rate proportion was estimated to be approximately 80-85% and we have > 80% power to detect reduction in the composite endpoint of approximately 23% with 60 per arm and a type II error rate of 5%, and 65 per arm assuming minimal dropout in the range of 5%. Since our estimates of dropout are extremely conservative (our reported dropout in EFIC studies is <1%)³² we are powered to detect changes in our primary composite endpoint as low as 21% if we actually observe little to no dropout. The secondary efficacy endpoint of iNO responsiveness is overpowered to detect a decrease in PA pressure in the region of 20-25 mm Hg with the planned enrollment.

2.5.2 Study Conduct Analysis

Continuous data will be summarized and compared using t-tests or a non-parametric equivalent should the normality assumption appear tenuous. Generalized linear mixed models, which account for non-independence of repeated assessments and endpoint structure, will be used to compare between iNO and placebo groups at multiple times. Analysis of the composite endpoint will be ascertained using an unadjusted two sample test of proportions with a type II error rate of 5%. In the event of imbalance of potential confounders after randomization an adjusted analysis will be performed using logistic regression with those unbalanced variables and treatment as the main effect of interest. Other secondary dichotomous outcomes will be summarized and compared by chi squared tests and appropriate exact methods should sample sizes be small. Time to event endpoints will be summarized by Kaplan Meir curves and compared using log rank tests. All tests will be two tailed with unadjusted $p < 0.05$ considered significant and performed using SAS 9.4.

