 - cardiac output based on aortic valve velocity (AV)
 - tricuspid annular plane systolic excursion (TAPSE)
 - left ventricular ejection fraction (EF).
- Absolute value at end of therapy (12h), change in value (12h vs 0h) and peak 24h post-ROSC troponin I
- Arterial blood gases at 0, 6, 12 and 24h after study drug initiation (when available)
- Upper body central venous oxygen saturation at 0, 6, 12 and 24h after study drug initiation (when available)
- Lactate at 0, 6, 12 and 24h after study drug initiation

Biochemical

- NO metabolites. Plasma nitrite, S-nitrosothiols and cyclic guanosine monophosphate (cGMP) levels obtained at 0, 3, 6, 9, 12h of study drug and 12h after cessation.
- RBC pellet for hemoglobin (Hb) studies (retained from above)
- MetHb at 6h (safety endpoint)
- Platelet mitochondria. Oxygen consumption rate, respiratory control ratio and superoxide generation (MitoSOX) at 0 and 12h of study drug when available. This data will be collected only when patients are enrolled from 6a-6p on weekdays (70/130 budgeted) to assure quality.
- Plasma for ascorbate 0, 3, 12, 24h
- Cardiolipin at 0, 3, 12, 24h
- After obtaining separate informed consent (IC) banked blood for DNA (pharmacogenetics)
- LSCI coupled to 1 and 5 min forearm vaso-occlusion at 0 h and 11 h. Endpoints will include ischemic trough, time to RH and RH peak, blood flow nadir 1 and 5 min after cuff release (respectively).

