2.5.3 Efficacy Analysis

Our primary outcome is intended to prove efficacy. Improvement in any of the secondary clinical outcomes being assessed would be considered preliminary evidence of efficacy requiring a subsequent larger trial for proof. Since iNO's effects on pulmonary vasodilation are best known, we will use this as our primary physiologic surrogate measure of iNO efficacy and will be compared using unadjusted two-sample tests or adjusted regression based methods.

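### Six continuous markers are each listed as a later value and as a change from 0h, with no lead form and no specified baseline adjustment; one pre-specified analysis per marker would be more precise, provided the ECHO baseline is defined first

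*Combined protocol and SAP*

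**What the plan says.** Section 2.4 gives each paired marker at least two forms.

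- ECHO (TRV, cardiac output, TAPSE, EF): "ECHO measures (absolute values at end of therapy (12h) and change in 12h vs 0h".
- Troponin I: "Absolute value at end of therapy (12h), change in value (12h vs 0h) and peak 24h post-ROSC troponin I".
- NSE: "Absolute value 24h after ROSC and change in value (24h vs 0h) of neuron specific enolase (NSE".

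That makes 4 × 2 + 3 + 2 = 13 comparisons on six markers. No form is named as leading.

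Section 2.5.2 sets the default test: "Continuous data will be summarized and compared using t-tests or a non-parametric equivalent should the normality assumption appear tenuous". Tests are two-sided at 0.05 without multiplicity adjustment. The same section adds a model for repeated measures: "Generalized linear mixed models, which account for non-independence of repeated assessments and endpoint structure, will be used to compare between iNO and placebo groups". It does not say how the 0h value enters. The one adjusted model it spells out is for a binary outcome: "In the event of imbalance of potential confounders after randomization an adjusted analysis will be performed using logistic regression".

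For pulmonary vasodilation, the primary physiologic surrogate, section 2.5.3 says results "will be compared using unadjusted two-sample tests or adjusted regression based methods". It gives no covariates, order or trigger.

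Two parts of section 2.2 matter here. The note under the visit table lets the 0h ECHO be acquired up to one hour after study drug has begun. Table 1 has troponin at 0, 6 and 12h, and NSE at 0 and 24h.

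**The concern.** These comparisons carry the synopsis aim on TRV and the trial's direct markers of heart and brain injury. One marker can yield several p-values: later value or change, t-test or rank test, and for the pulmonary measure adjusted or not. Nothing in the plan ranks them, so the one reported could be chosen after the results are seen.

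The plan also gives up precision. The 0h values are already scheduled, but neither planned form makes the best use of them. That matters more because section 2.2 expects many secondary measurements to be missing, and ECHO and NSE are not among the items marked as essential.

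**Working it through.** **The plan's own figures.** Section 2.5.1 gives no power, SD or baseline correlation for ECHO, troponin or NSE. Its remark on PA pressure (20-25 mm Hg) has no SD and cannot be reproduced. The calculation for the composite can: 60 per arm and a 23-point reduction from 82.5% give 80.1% power (78.1% from 80%, 82.3% from 85%; two-sided alpha 0.05). From it I take only the 65 per arm.

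**Inputs.** From the documents: 65 per arm, 1:1 allocation, two-sided 0.05. Assumed: correlation r between 0h and later value of 0.3, 0.5 or 0.7; equal variances at both times; a true difference of 0.5 SD; complete data.

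**Step 1, clean baseline.** Relative error variances are 1 for the later value, 2(1 − r) for the change and 1 − r² for ANCOVA. Power uses the noncentral t with noncentrality 0.5/√(2v/65), v being the relative variance. At r = 0.5:

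- later value and change: v = 1, 0.5/0.175 = 2.85, power 81%;
- ANCOVA: v = 0.75, 0.5/0.152 = 3.29, power 90%.

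| r | variance: later / change / ANCOVA | ANCOVA below the better of the two | power: later / change / ANCOVA |
|---|---|---|---|
| 0.3 | 1 / 1.40 / 0.91 | 1 − 0.91/1 = 9% | 81% / 67% / 84% |
| 0.5 | 1 / 1.00 / 0.75 | 1 − 0.75/1 = 25% | 81% / 81% / 90% |
| 0.7 | 1 / 0.60 / 0.51 | 1 − 0.51/0.60 = 15% | 81% / 95% / 98% |

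The direction does not depend on r. We have 1 − r² < 1 whenever r is not 0, and 2(1 − r) − (1 − r²) = (1 − r)² > 0 whenever r < 1. The size does depend on r: the gain over the later value is only 4% at r = 0.2, and over the change only 5% at r = 0.9.

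**Step 2, two tests per marker.** The two statistics correlate √((1 − r)/2), which is 0.59, 0.50 and 0.39. By the bivariate normal, the chance that at least one is falsely significant is 8.8%, 9.1% and 9.4%, against 5% for a single test. With a true 0.5 SD difference, exactly one of the two is significant in about 26%, 21% and 19% of trials.

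**Step 3, skewed markers.** This is a simulation with log-SD 1.3, a 40% reduction, 60 per arm and r from 0.4 to 0.8 (all assumed). Log-scale ANCOVA has 62-95% power. A rank test on the later value has roughly 55%, whatever r is. Change-score power depends on the rise from 0h to the later time in controls, also assumed:

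- no rise: t-test 18-38%, rank test 34-76%;
- threefold rise: t-test 32-51%, rank test 52-86%.

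Log-scale ANCOVA leads in both scenarios.

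**Step 4, ECHO with a late 0h scan.** Suppose a fraction f of the drug effect is already present in every 0h scan. ANCOVA then estimates d(1 − rf) and the change score d(1 − f), where d is the true difference. At f = 0.5 and r = 0.5, ANCOVA has 0.375/0.152 = 2.47, power 69%; the change score has 0.25/0.175 = 1.43, power 29%.

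| r | later value | ANCOVA, f = 0.5 | change, f = 0.5 | ANCOVA, f = 1 |
|---|---|---|---|---|
| 0.3 | 81% | 71% | 22% | 55% |
| 0.5 | 81% | 69% | 29% | 37% |
| 0.7 | 81% | 73% | 45% | 22% |

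The documents give neither f nor the share of late scans. All scans late is the worst case.

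**The case against.** The best defence is that the plan already contains most of the remedy. The mixed models of section 2.5.2 could cover troponin, which has 0, 6 and 12h draws. Section 2.5.3 allows adjusted regression for the pulmonary surrogate. The non-parametric fallback would probably keep a raw t-test away from badly skewed markers. Section 2.5.3 treats improvement in secondary clinical outcomes as preliminary evidence only, and section 2.2 describes the secondary data as mechanistic and hypothesis-generating.

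Much of this stands, and it rules out some stronger readings.

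- A reader might infer that the planned tests ignore the baseline. Only the later-value test does; a change score uses the 0h value, though inefficiently.
- A reader might infer that the plan provides no adjustment at all. It permits adjustment for the pulmonary measure, and the mixed model may allow it for troponin. The fault is that neither is specified.
- A reader might infer that ANCOVA is always the stronger choice. For ECHO that fails if 0h scans are taken after drug start: the unadjusted 12h value is then the only form free of that bias. The same problem harms the change score more, so it does not rescue the current pair of endpoints.

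What the defence does not answer is that no lead form is named for any of the six markers, and that ECHO and NSE, with one post-baseline value each, fall to the unadjusted default.

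**Conclusion.** The point holds for the secondary continuous markers. Each has competing forms and no lead analysis, and the default tests have no baseline covariate. With a clean baseline, both planned forms are less precise than ANCOVA for every r between 0 and 1; at r = 0.3 to 0.7 the variance is 9-25% below the better of the two. For troponin and NSE this is a gain from measurements already scheduled. For ECHO it is a gain only with scans that precede study drug.

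It would be wrong to conclude that the trial's main result is at risk or that the planned tests are invalid. The composite has its own analysis, and a randomized comparison of later values is sound, only inefficient. The change should be made, but it is not critical.

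The direction in the clean-baseline case rests on equal variances. The power figures also rest on assumed r, effect size, log-SD, rise from 0h and complete data, none of which the documents give. Missing ECHO or NSE values would lower all of them.

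**What to change.** 1. Name one lead analysis per marker in sections 2.4 and 2.5.2, and make the change scores descriptive.
2. For NSE (24h) and troponin (12h), use ANCOVA on the log scale with treatment, the log 0h value and centre (the stratification factor), and report the ratio of geometric means. For troponin, the mixed model of section 2.5.2 is an alternative if the 0h value is a covariate; choose one in advance. State the role of the 24h troponin peak.
3. For ECHO, including TRV, define baseline first. Record the scan time relative to study drug start, count only earlier scans as baseline, and treat later ones as missing baseline, for example with a missing-baseline indicator. Section 2.5.5 excludes imputation, so say that this concerns a covariate and not an outcome. Then use ANCOVA of the 12h value, with the unadjusted 12h comparison as the sensitivity analysis.
4. In section 2.5.3, replace the open choice ("compared using unadjusted two-sample tests or adjusted regression based methods") with the rule in item 3.
5. If power is quoted for these markers, list the assumptions behind it.

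The cost is analysis-plan wording and one recorded time per ECHO. No new measurement is needed. The ECHO gain shrinks as the share of late scans grows.
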